10.3. Statistical methods

10.3.1. Basic method

Part I

The PK profile will be characterized and safety and tolerability will be evaluated based on Cycle 1 data. In addition, preliminary efficacy (prevention of myelosuppression) data will be summarized.

Part II

It is mainly used to verify the effectiveness of Trilaciclib treatment (prevention of bone marrow suppression). The primary endpoint was DSN in Cycle 1. Unless otherwise specified, efficacy endpoints will be analyzed in the FAS. Some of these endpoints may be analyzed based on the PP. Descriptive statistics for continuous data will include means, medians, standard deviations and ranges, and categorical data will provide counts and percentages. Time-to-event data will be analyzed using the Kaplan-Meier method.

Detailed statistical methods, including sensitivity analyses, handling of missing values, etc, will be presented in the Statistical Analysis Plan (SAP).

10.3.2. Summary of study conduct

Study enrollment, medications, reasons for discontinuation, and reasons for discontinuation will be summarized by treatment group. Major protocol deviations, including those for inclusion and exclusion criteria, will be listed and summarized by treatment group.

10.3.3. Treatment group comparability summary

For demographics (including age, gender, etc.) and baseline characteristics (including baseline conditions, etc.), continuous variables will be summarized using descriptive statistics (mean, standard deviation, median, range, etc.) and categorical variables will be summarized using counts and proportions, as appropriate.

Unless otherwise specified, baseline measurements are defined as the last available valid measurement prior to the first dose.

10.3.4. Primary efficacy endpoint analysis

The primary endpoint was DSN in Cycle 1. For subjects with at least 1 occurrence of severe neutropenia (SN) in Cycle 1, Cycle 1 DSN was defined as the number of days from the date of the first ANC value $< 0.5 \times 10^9$ /L to the date of the first ANC value $\ge 0.5 \times 10^9$ /L. Where the date of the first ANC value $\ge 0.5 \times 10^9$ /L met the following requirements: (1) occurred after the ANC value was $< 0.5 \times 10^9$ /L, and (2) there were no other ANC values $< 0.5 \times 10^9$ /L between this date and the end of Cycle 1 (otherwise, if this subject entered Cycle 2, it was counted as Day 1 of Cycle 2). If the subject did not experience any SN during Cycle 1, Cycle 1 DSN was scored as 0.

Nonparametric analysis of covariance (Nonparametric ANCOVA) will be used to evaluate the efficacy of Cycle 1 DSN. Mean differences between treatment groups, standard errors, and their 95% confidence intervals based on Satterthwaite t tests were also provided.

Detailed definitions, handling of missing values, and detailed analysis methods for Cycle 1 DSNs will be provided in the SAP.

10.3.5. Secondary efficacy endpoint analyses

Key secondary efficacy endpoints

Key secondary efficacy endpoints included SN occurrence, occurrence of red blood cell transfusion (on/after Week 5), occurrence of use of granulocyte colony-stimulating factor (G-CSF), composite endpoint - major hematological adverse events, etc. Descriptive statistics will be used for summarization. Descriptive statistics for continuous data will include mean, median, standard deviation and range. Categorical data will provide counts andpercentages, and the differences between groups and their 95% confidence intervals will be estimated.

Other secondary efficacy endpoints

Other secondary efficacy endpoints included the occurrence of grade 3/4 hematologic toxicities, trough absolute neutrophil count at each cycle, absolute neutrophil count, platelet count, absolute lymphocyte count, and hemoglobin over time, occurrence of ESA use, occurrence of recombinant human interleukin-11 use, occurrence of thrombopoietin (TPO) use, occurrence of intravenous or oral antibiotics, occurrence of serious infectious adverse events, occurrence of serious pulmonary infection adverse events, occurrence of febrile neutropenia, occurrence of platelet transfusions (during chemotherapy), objective tumor response rate (ORR), and disease control rate (DCR). Descriptive statistics will be used for summaries. Descriptive statistics for continuous data will include means, medians, standard deviations, and ranges, and categorical data will provide counts and percentages.

Detailed analysis methods for key secondary efficacy endpoints and other secondary efficacy endpoints will be presented in the SAP.

10.3.6. Safety analysis

Safety analyses will be based on the Safety Analysis Set. Safety evaluations included monitoring of treatment emergent adverse events (TEAEs), physical examinations, vital sign measurements, electrocardiograms (ECGs), and clinical laboratory tests (hematology, blood chemistry, and urinalysis) throughout the treatment period.

Descriptive statistics will be used to analyze adverse events, laboratory test indicators, vital signs and ECG, and summarized according to the treatment groups actually received.

Extent of exposure will be summarized as duration of treatment and dose of study drug taken during the treatment period.

According to the vital signs data at baseline and each visit time point, each indicator of vital signs at each visit time point and the change from baseline were statistically summarized.

According to the laboratory test results at baseline and each visit time point, the results of laboratory test items completed at each visit time point and the positive and abnormal changes from before treatment were statistically summarized.

Only treatment-emergent adverse events were counted. A TEAE was defined as an untoward medical occurrence that emerged during treatment or worsened relative to pretreatment. All AEs will be coded according to the International Conference on Harmonisation (ICH) Medical Dictionary for Regulatory Activities (MedDRA) and the number and incidence will be summarized by System Organ Class (SOC), Preferred Term (PT) and investigational product grouping. List the serious adverse events after medication, adverse

events leading to drug withdrawal, adverse events leading to dropout and drug-related adverse events, and describe the details of each adverse event/adverse reaction in each subject in a separate table, including the type, severity, occurrence and duration, outcome of adverse events as well as their relationship with the investigational drug and the dose of the drug.

Concomitant medications will be reported using summary tables.

10.3.7. Pharmacokinetic analysis

The first part of the pharmacokinetic analysis included PK concentration analysis and PK parameter analysis.

PK concentration analysis: PK concentration data will be summarized and listed by treatment group according to each scheduled sampling time point as defined in the protocol. Mean and median drug concentration-time profiles (linear and semi-log plots) are also plotted. Individual PK concentration data from subjects will be plotted (linear and semi-log plots) against drug concentration versus time by treatment group and analyte according to actual sampling time. Statistical analysis of PK concentrations will be based on the PK Analysis Set.

PK Parameter Analysis: Statistical analysis of PK parameters will be summarized descriptively based on the PK Analysis Set.

Population pharmacokinetic analyses will be exploratory based on the data obtained.

Detailed analysis methods will be given in the SAP. Population pharmacokinetic analysis methods will be presented in an independent population pharmacokinetic analysis plan.

10.3.8. Data analysis time

When the subjects in Part I have completed safety and PK assessments in Cycle 1, an analysis will be performed to characterize the PK profile and evaluate the safety and tolerability based on Cycle 1 data. In addition, preliminary myeloprotective efficacy (prevention of chemotherapy-induced myelosuppression) data will be summarized. Data from subjects in Part I may be updated synchronously until the end of the study at the time of data analysis in Part II.

The primary analysis will be performed at the end of Cycle 1 for randomized subjects in Part II. The sponsor 's necessary personnel will be unblinded, but the investigator, subject, and other personnel will remain blinded. The primary measure of myeloprotective efficacy, duration of severe neutropenia (DSN) in Cycle 1, as well as other applicable secondary or exploratory endpoints, will be assessed based on unblinded data.

The second analysis in Part II will be performed after all randomized subjects have completed 6 cycles or end of treatment.

The final analysis of Part II will be performed at the end of the study.

10.3.9. Exploratory analyses

Descriptive statistics will be used to summarize exploratory endpoints, progression-free survival (PFS), overall survival (OS), population pharmacokinetic characteristics, etc. Detailed analysis methods will be presented in the SAP.

The analysis methods for population pharmacokinetics will be presented in a separate SAP analysis plan for population pharmacokinetics.

Exploratory analyses may not be included in the clinical study report based on actual circumstances.

11. Supporting documentation and clinical operations related considerations

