diagnosis. Major diagnosis and treatment guidelines at home and abroad (including those edited by Chinese Society of Clinical Oncology) recommend platinum-based combination with or without PD-L1 antibody as first-line standard treatment for SCLC, while topotecan is recommended for second-line chemotherapy. Studies have shown that platinum-based combination therapy with etoposide or topotecan is associated with significant myelosuppression in extensive stage SCLC (neutropenia 47% to 92%, leukopenia 8% to 66%, thrombocytopenia 10% to 46%, and anemia 7% to 34%). In Asian populations (including China, Korea, Japan), the occurrence of myelosuppression caused by platinum-based and etoposide chemotherapy was similar. Literature have shown that chemotherapy-induced myelosuppression (grade 3/4 neutropenia 5.6% ~ 93.8%, anemia 2.9% ~ 33.3%, thrombocytopenia 3.2% ~ 33.3%) is always the main adverse reaction to be urgently addressed in Asian populations, including China, South Korea, and Japan, for patients with small cell lung cancer treated with carboplatin/cisplatin combined with etoposide effects or topotecan. Myelosuppression is an important cause of many adverse events in cancer chemotherapy, such as infection, sepsis, bleeding, and fatigue, leading to hospitalization or the use of hematopoietic growth factors or the need for red blood cell and/or platelet transfusions. In addition, myelosuppression often leads to chemotherapy dose reductions or limits in treatment dose intensity, rendering patients unable to derive greater benefit from chemotherapy.

Trilaciclib is a highly potent, selective, reversible CDK4/6 inhibitor in clinical development to protect bone marrow by protecting hematopoietic stem and progenitor cells (HSPCs) when administered systemically. The proliferation and differentiation of HSPCs is very dependent on CDK4/6 activity and is arrested in G1 phase of the cell cycle when exposed to appropriate doses of Trilaciclib, thus avoiding damage by cytotoxic chemotherapeutic agents of the cell cycle. Therefore, for CDK4/6-independent tumors (such as small cell lung cancer, etc.), Trilaciclib combined with chemotherapy can protect the bone marrow without antagonizing the anti-tumor efficacy of chemotherapy.

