2.1. Study objectives

Part I (Safety Run-in and PK Evaluation Part):

Primary objective

- To evaluate the pharmacokinetic (PK) profile of Trilaciclib in patients with extensive stage small cell lung cancer;
- To evaluate the safety and tolerability of Trilaciclib in patients with extensive stage small cell lung cancer;
- To evaluate the effectiveness of Trilaciclib (prevention of chemotherapy-induced myelosuppression) in patients with extensive stage small cell lung cancer;

Secondary objectives

- To comprehensively evaluate the myeloprotective effect of Trilaciclib in patients with extensive stage small cell lung cancer;
- To evaluate the short-term antitumor efficacy of Trilaciclib in patients with extensive stage small cell lung cancer;

Exploratory objectives:

- To evaluate the long-term antitumor efficacy of Trilaciclib in patients with extensive stage small cell lung cancer;
- Population pharmacokinetic profile.

Part II (randomized, double-blind part):

Primary objective

• To evaluate the effectiveness of Trilaciclib (prevention of chemotherapy-induced myelosuppression) in patients with extensive stage small cell lung cancer;

Secondary objectives

- To comprehensively evaluate the myeloprotective effect of Trilaciclib in patients with extensive stage small cell lung cancer;
- To evaluate the safety and tolerability of Trilaciclib in patients with extensive stage small cell lung cancer;
- To evaluate the short-term antitumor efficacy of Trilaciclib in patients with extensive stage small cell lung cancer;

Exploratory objectives:

- To evaluate the long-term antitumor efficacy of Trilaciclib in patients with extensive stage small cell lung cancer;
- Population pharmacokinetic profile.

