- Occurrence of infectious serious adverse events;
- Occurrence of lung infection SAEs:
- Occurrence of febrile neutropenia;
- Occurrence of platelet transfusion;
- Safety and tolerability: adverse events, laboratory abnormalities, etc.;
- Objective tumor response rate (ORR);
- Disease control rate (DCR).

Exploratory Endpoints

- Progression-free survival (PFS);
- Overall survival (OS);
- Population pharmacokinetic profile.

3. Study design

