4.5.2. Progression Free Survival and Overall Survival Analysis

Exploratory analyses of progression-free survival (PFS) will be performed based on the FAS. PFS is defined as the time from the date of randomization to the first documented radiologically disease progression (according to RECIST1.1) or death due to any cause, whichever occurs first. In the absence of disease progression and death at the time of analysis, PFS will be censored at the date of last tumor assessment; in the absence of a valid postbaseline tumor assessment, PFS will be censored at the date of the date of the date of randomization.

Exploratory analyses of overall survival (OS) will be performed based on the FAS. OS is defined as the time from the date of randomization to death of the patient for any cause; for patients who have not died at the time of analysis, OS will be censored at the date last known to be alive .

PFS and OS rates at various time points will be estimated using the Kaplan-Meier method,

and 95% CI will be provided using Greenwood 's method. The Kaplan-Meier method will also be used to estimate 25%, median, and 75% time (months) for PFS and OS, and the Brookmeyer-Crowley method will be used to calculate the 95% CI and survival curves for PFS and OS will be provided. The HR and its 95% CI will be calculated between the two treatment arms (Trilaciclib versus placebo) based on a stratified Cox proportional hazards model with treatment arm and IRT-based randomization stratification factors as fixed effects. Two-sided P values will be calculated from stratified log-rank test.

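### Protocol 10.3.9 lets PFS and OS, the trial's only time-to-event tumour-control data, be left out of the clinical study report with no criterion or deadline

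*Protocol*

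**What the plan says.** Protocol 10.3.9 opens with the endpoints it covers: "Descriptive statistics will be used to summarize exploratory endpoints, progression-free survival (PFS), overall survival (OS), population pharmacokinetic characteristics, etc". It leaves detailed methods to the SAP and sends population PK to a separate plan. It then closes with "Exploratory analyses may not be included in the clinical study report based on actual circumstances". No criterion, responsible party or time point is attached to that sentence.

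Protocol 2.1 sets two antitumor objectives for Part II. The secondary one is "To evaluate the short-term antitumor efficacy of Trilaciclib in patients with extensive stage small cell lung cancer". The exploratory one is "To evaluate the long-term antitumor efficacy of Trilaciclib in patients with extensive stage small cell lung cancer". Section 2.2 lists ORR and DCR as secondary endpoints and PFS and OS as exploratory ones.

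Protocol 10.3.8 plans three Part II analyses: at the end of Cycle 1, after six cycles or end of treatment, and at end of study. The necessary sponsor personnel are unblinded at the first of these, and applicable exploratory endpoints may be assessed on unblinded data at that point.

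SAP 4.5.2 states: "Exploratory analyses of overall survival (OS) will be performed based on the FAS". It says the same of PFS. It gives definitions, censoring rules, Kaplan-Meier estimates, a stratified Cox hazard ratio with 95% CI, and a stratified log-rank P value. It does not say where, or whether, these will be reported.

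**The concern.** The rationale for giving a CDK4/6 inhibitor before chemotherapy is set out in the background part of the protocol synopsis: "Trilaciclib combined with chemotherapy can protect the bone marrow without antagonizing the anti-tumor efficacy of chemotherapy". In this trial PFS and OS are the randomised time-to-event evidence on that premise. A clause that makes their appearance in the clinical study report discretionary, with no rule fixed in advance, permits reporting that depends on the result. If that happened, the benefit-risk conclusion would rest on a report from which an unfavourable survival estimate could be missing. A favourable estimate that did appear would also be hard to interpret, because the reader could not tell whether it would have been shown had it gone the other way.

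**Working it through.** The documents give no figure for this point, so the main check is a comparison of texts.

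**1. Does the clause reach PFS and OS?** Yes. Section 10.3.9 names them as exploratory, Protocol 2.2 lists them as exploratory, and SAP 4.5.2 uses the same label.

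**2. Does it reach other tumour-control data?** No. ORR and DCR are secondary (Protocol 2.2 and 10.3.5). SAP 4.5.1 gives ORR a CMH-weighted difference between arms with 95% CI and an exact P value, gives both rates Clopper-Pearson intervals, and adds waterfall, time-line and swimming plots.

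**3. Can the choice follow the results?** Section 10.3.9 sets no time for it, and section 10.3.8 unblinds sponsor personnel well before the final analysis. A late choice is therefore possible. No text says that one is planned.

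**4. Does the SAP close the gap?** Only in part. It fixes that the analyses are done and how, but not that they are reported. It is also written to Protocol V1.3, whereas the protocol reviewed is V1.4.

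**5. Do the unaffected data substitute?** Not fully.
- ORR and DCR use the response-evaluable set, which requires at least one post-treatment scan (SAP 4.2.2). Patients who die or deteriorate before a scan are not in it. PFS and OS use the FAS.
- Response shows neither durability nor survival.
- Treatment-emergent events stop at 30 days after the last dose or at new anticancer therapy (SAP 4.6.2), so later deaths would appear mainly through OS.

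**Illustration of precision.** The number of Part II deaths at the final analysis is an assumption. Protocol 3.4 ends the study at 75% deaths, 12 months after last enrolment, or sponsor decision, whichever is first. Footnote c of Tables 11 and 12 runs survival follow-up until 50% of subjects have died. Applied to the 80 Part II patients:
- 0.75 × 80 = 60 deaths
- 0.50 × 80 = 40 deaths

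With 1:1 allocation, SE(log HR) = 2/√d.

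| Quantity | d = 40 | d = 60 |
|---|---|---|
| SE = 2/√d | 0.316 | 0.258 |
| 95% CI factor = exp(1.96 × SE) | 1.86 | 1.66 |
| 95% CI if observed HR = 1.0 | 0.54 to 1.86 | 0.60 to 1.66 |
| P(observed HR ≥ 1.2, true HR 1.0) = P(Z > 0.182/SE) | P(Z > 0.58) = 0.28 | P(Z > 0.71) = 0.24 |
| Geometric-mean HR if only estimates ≤ 1.0 were reported = exp(−0.798 × SE) | 0.78 | 0.81 |

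Here 0.182 = ln 1.2, and 0.798 is the mean of the absolute value of a standard normal variable. The last row rests on a hypothetical reporting rule that appears nowhere in the documents. It shows what selection of that kind would do and does not predict what this plan will produce.

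**The case against.** The strongest reply is that the sentence has an innocent purpose. Reporting is staged, PFS and OS will be immature at the end of Cycle 1, and section 10.3.8 itself speaks only of applicable exploratory endpoints. The sentence also directly follows the one that sends population PK to its own plan. Leaving immature or separately planned analyses out of a given report would fit the wording. This reading is plausible and the fix should allow for it. But the text is not confined to it: as written, the sentence covers the final PFS and OS results equally.

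A second reply is that the analyses themselves are not discretionary, since SAP 4.5.2 prespecifies them in detail. That stands, and it limits selective analysis. What remains is a gap in reporting.

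A third reply is that so few deaths make the hazard ratio uninformative. Precision is indeed low: by the Schoenfeld formula, power to detect a true HR of 1.5 is Φ(ln 1.5 × √d/2 − 1.96), about 25% at 40 deaths and 35% at 60. That is a reason to show the estimate with its interval and interpret it cautiously. It is not a reason to make its appearance optional.

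Two stronger readings are tempting and are not supported. A reader might infer that PFS and OS are the only data on whether trilaciclib weakens tumour control. They are not, because ORR and DCR lie outside the clause and ORR is compared between arms. A reader might also infer that the omission decision will be taken after unblinding, or is meant to hide a result. No section says when or by whom it is taken. The documents only fail to prevent a late choice.

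**Conclusion.** The point holds as a matter of reporting. Protocol 10.3.9 affirmatively permits PFS and OS to be left out of the clinical study report without a criterion or deadline, and the SAP does not withdraw that permission. The scope is limited to the only time-to-event tumour-control data and the only endpoints for the long-term antitumor objective. Data collection and type I error are untouched, as are the primary, key secondary and response analyses.

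The numerical illustration assumes that the death percentages apply to the 80 Part II patients. Neither percentage is restricted to Part II in the text, and the 12-month or sponsor-decision limbs of Protocol 3.4 could stop the study with fewer than 40 deaths, so the range is not a bound. The conclusion does not depend on it. This is an improvement available at almost no cost, not a defect in the trial's main inference.

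**What to change.** Limit the last sentence of Protocol 10.3.9 to population PK, which has its own analysis plan (Protocol 10.3.7 and 10.3.9, SAP 4.10). Add that PFS and OS as defined in SAP 4.5.2 will be reported by arm at the final analysis, with number of events, hazard ratio and 95% CI, in the clinical study report or an addendum to it, whatever the result. State that an earlier staged report may defer them as immature. Repeat the commitment in SAP 4.5.2 when the SAP is aligned with Protocol V1.4.

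At the same time, reconcile the 50% stop for survival follow-up in the flow-chart footnotes with the 75% limb of the end-of-study definition, because together they determine how many deaths the OS analysis will have.

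The cost of the main change is one sentence. It needs no new patients, visits, data or analyses.

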11.1. Management of study drug

11.1.1. Dosage form, appearance, packaging, and labeling of study drug

Trilaciclib is supplied as a sterile powder in packaging and labeling information according to local laws and regulations and is labeled for clinical trial use only.

Placebo was formulated as the vehicle for Trilaciclib – 250 mL of 5% dextrose in water or saline (0.9% sodium chloride)

Packaging and labeling information for carboplatin, etoposide, and topotecan are detailed in the package insert.

